9.5 Study Size

Gaucher Disease is a rare disease, therefore no restriction on the number of participants will be made. In other words, all patients with GD1 and taking eliglustat will be included in the analysis. This will allow to maximise the statistical power and to minimise the small cell/identifiability issue. Indeed, this problem may arise due to the small number of patients with GD1.

Knowing that the SNDS covers 99% of the French population, the Danish GD registry covers all the Danish population, the GePaRD database covers about 25 million of Germans and the Maccabi database covers approximately 2.5 million Israelis, the DUS will cover approximately 100 million people.

According to estimated number of patients taking eliglustat in each data source, the expected minimum number of participants in the DUS is 128 (87 in the SNDS, 10 in Danish GD registry, 11 in GePaRD and 20 in Maccabi database).

9.6 Data Management

[figure not shown]
The selected registries have already participated in other DUS or post-authorisation safety studies (PASS), required by EMA or by the national or local health authorities.

The data management process is depicted in Figure 1.

In each data source, GD1 patients treated with eliglustat will be extracted into a working database whose format is adapted to receive raw prescription data. In the working database, variables will be re-coded and aligned in order to have one line of data per patient. The creation and re-working of variables will follow locally defined procedures and requirements (e.g., access to non-anonymised data limited to database personnel). Then, the working database will be pseudo-anonymised according to local requirements and the European Directive of personal data protection. This pseudo-anonymised database will become the analysis database with all needed variables for data analyses according to the objectives of the DUS. This database will be in a SAS- or R-compatible format.

Due to data protection issue, data from the selected data sources cannot be gathered in a single place and analysed by a single team. Therefore, a statistical programme in SAS or R will be written by (or in close collaboration with) the Parexel statisticians or statistical programmers and applied on their analysis database. Where Parexel is responsible for writing the programmes, the programmes may be transferred to each data source to be applied on their database. For the French data, after approval of the study by the regulatory authority, the analyses will be directly conducted by the statisticians from RCTs, subcontractor from Parexel, on data posted in a dedicated server of the SNDS. For the Danish and Israelian data, since there is no statistician in these data sources, Parexel statisticians will conduct analyses either on-site or through a secured virtual private network (VPN) access. Finally, statistical results obtained in each data source will be transferred to Parexel, assembled in tables and included in the final report.

Figure 1 Data flow

Abbreviations: GD1 = Gaucher Disease Type 1

9.7 Data Analysis

A separate SAP and country-specific ADS documents will be produced, providing detailed methods for the analyses outlined below.

Any deviations from the planned analyses will be described and justified in the final study report.

9.7.1 General Considerations

The exposure period for one patient corresponds to the period of eliglustat use. This period will be defined as the period between the exposure start date (the first record of eliglustat prescription) and the exposure end date (end of study or date of the last eliglustat prescription plus the duration of eliglustat use according to the last prescription or death date).

The statistical analyses will be only descriptive and will include the following:

• Descriptive analysis of eliglustat therapy in terms of duration and dose.

- Descriptive analysis of the past medication use (one year prior to the exposure period) in terms of proportion, therapeutic class and duration. The treatments of interest will be (details in Appendix 1 in Section 14.1):
 - Strong and moderate CYP2D6 inhibitors (CMI1 and CMI2)
 - Strong and moderate CYP3A inhibitors (CMI3 and CMI4)
 - Simultaneous use of strong or moderate CYP3A inhibitors with strong or moderate CYP2D6 inhibitors (CMI1 + CMI2 + CMI3 + CMI4)
 - Strong CYP3A inducers (CMI5)
 - P-gp substrates (CMI6)
 - CYP2D6 substrates (CMI7)

The proportions will be computed taking into account all treatments of interest and also by type of treatments and by duration. Proportions for the group CYP inhibitors will be also computed. The duration will be treated as a continuous variable and also as a categorical variable. The categorical variable will be defined as follow: 1. Total use will be defined as any prescription whatever the duration; 2. Chronic use will be defined as total duration of single or consecutive prescriptions of 15 days or over.

If the number of GD1 patients allows it, stratified analyses based on gender and age groups will be performed as well as analyses by year.

- Descriptive analysis of the concomitant medication use (i.e., during the exposure period) in terms of proportion, therapeutic class and duration. The treatments of interest will be the same as for the past medication use. The proportions will be computed as for the past medication use that is considering all treatments and also by therapeutic class and duration.
- Descriptive analysis of the health care service pattern (i.e., prescriber's specialty and types of patient visit) for the use of concomitant medications.

Analyses will be conducted on the whole period of study for each data source separately for data protection reasons. This will allow to compare the drug availability and prescribing patterns between European countries.

If the number of GD1 patients taking eliglustat allows it, stratification analyses based on sex and age will be performed as well as analyses by year with trends in proportions over time.

9.7.2 Control of Bias and Confounding

This DUS is a descriptive study, therefore confounding will not be examined. Only age and sex will be considered and used for stratification if sufficient participants are included in the study (i.e., in absence of small cell).

9.7.3 Analysis of Primary Endpoint

9.7.3.1 Dose of Eliglustat

The dose of eliglustat will be reported as a categorical variable since only two dosages exist: one capsule per day (i.e., 84 mg/day) and two capsules per day (i.e., 168 mg/day). A third category, other, will be created for patients that would not fit in the two previous categories for any reasons. Number and percentage of patients in each category will be reported.

9.7.3.2 Duration of Eliglustat

Using the duration of eliglustat use of all GD1 patients, a mean duration will be computed together with dispersion.

Patients will be also classified in three categories according to their eliglustat duration: <1 year, 1-<2 years and ≥ 2 years. Number and percentage of patients in each category will be reported. These categories may change depending on results in each data source.

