8.1 Primary Objective

The primary objective of the DUS is to estimate the dose and duration of eliglustat therapy as well as the proportion, therapeutic class, and duration of past and concomitant medication use in patients treated with eliglustat. The concomitant medications of interest (CMI) are strong and moderate CYP2D6 inhibitors, strong and moderate CYP3A inhibitors, strong CYP3A inducers, P-gp substrates and CYP2D6 substrates (Appendix 1 in Section 14.1). Simultaneous use of strong or moderate CYP2D6 inhibitors with strong or moderate CYP3A inhibitors concomitantly with eliglustat will be explored, if feasible.

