9 RESEARCH METHODS

9.1 Study Design

The DUS of eliglustat will be undertaken in a series of prescription databases covering large populations to provide useful and reliable investigations of diseases as rare as Gaucher Disease. This DUS will be based on secondary use of data. This DUS is descriptive only with no comparative elements.

The study shall take the form of a cohort study using electronic health records. Gaucher Disease Type 1 patients identified in each prescription database who are being prescribed eliglustat will be followed from one year before their first prescription of eliglustat to the end of the study in Q3 2024. During this period, all prescriptions of past and CMI will be recorded (Appendix 1 in Section 14.1). The study will rely entirely on analysis of secondary data as described in the initial study synopsis submitted in the Risk Management Plan (RMP).

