9.2 Setting

9.2.1 Study Period

The study period will begin from one year before the first prescription of eliglustat in each data source to the end of the study.

The date of the first prescription of eliglustat will vary between data sources since the launching/reimbursement of eliglustat is different in each country (see Section 9.4). In any case, the first prescription will be after the date of approval of eliglustat by the EMA that is 19 January 2015.

The exposure period for one patient will be defined as the period between the exposure start date (date of the first record of eliglustat prescription) and the exposure end date, i.e., the date of the last eliglustat prescription plus the duration of eliglustat use according to the last prescription or the end of the study or the death of the patient if it occurs before the end of the study.

The end date of the study period will also vary between data sources since different time-lag exist between the time of prescription/delivery of drugs and availability of these data in databases. Consequently, in case of a two-year time-lag, data extracted in 2022 will have been collected until 2020 thus, the study period will end in 2020.

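### The mean eliglustat duration treats patients still on drug at data end as if they had stopped, so as an estimate of duration of therapy it is biased short by an amount the documents do not fix

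*Protocol*

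**What the plan says.** Section 8.1 makes duration a matter of estimation: "The primary objective of the DUS is to estimate the dose and duration of eliglustat therapy". Section 9.1.1 lists duration of eliglustat use among the primary outcomes.

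The exposure end date is defined twice. Section 9.2.1 takes the last prescription "plus the duration of eliglustat use according to the last prescription or the end of the study or the death of the patient". Section 9.7.1 gives the alternatives as "end of study or date of the last eliglustat prescription plus the duration of eliglustat use according to the last prescription or death date". Under both, reaching the end of the data closes a patient's exposure in the same way as a real stop.

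Section 9.7.3.2 then states the summary: "Using the duration of eliglustat use of all GD1 patients, a mean duration will be computed together with dispersion". It adds: "Patients will be also classified in three categories according to their eliglustat duration", namely under 1 year, 1 to under 2 years, and 2 years or more. Of these classes it says: "These categories may change depending on results in each data source".

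The end of observation is described in two ways. Section 9.1 says that patients "will be followed from one year before their first prescription of eliglustat to the end of the study in Q3 2024". Section 9.2.1 says that the end varies by source and gives a two-year lag as an example: "data extracted in 2022 will have been collected until 2020 thus, the study period will end in 2020".

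**The concern.** Eliglustat is indicated for long-term treatment (section 7.1). Patients may start at any time after launch, and one prescription is enough for inclusion (section 9.2.2), so there is no minimum follow-up. The duration of anyone still treated at data end is right-censored. Section 9.7.3.2 pools these truncated values with completed ones and does not tell them apart.

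Three consequences follow.

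- The mean falls below the true duration of therapy.
- A patient who started less than 2 years before data end cannot be classed as 2 years or more, however persistent.
- Launch dates and data lags differ by country, so sources with the same persistence can show different durations. Section 9.7.1 nevertheless expects the separate analyses to allow comparison of prescribing patterns between countries.

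Letting the categories follow the results in each source weakens that comparison further. Section 9.9 states that no sources of bias could affect the results, so a reader would not be warned.

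**Working it through.** **The plan's own figure.** The only size figure is the expected minimum in section 9.5: 87 + 10 + 11 + 20 = 128, which adds up. The protocol gives no expected duration, discontinuation rate or start pattern, so those are assumptions here.

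**Windows.** Launch dates are from section 9.4. Data-end dates are assumed from the lags stated there.

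| Source | Launch | Assumed data end | Window W (years) |
|---|---|---|---|
| France | 9 Nov 2016 | end 2023 (year N available in N+1) | 7.14 |
| Denmark | April 2015 | Q3 2024 (no lag) | 9.46 |
| Germany | 15 April 2015 | end 2020 (full two-year lag, 2022 extraction) | 5.71 |
| Israel | 12 Jan 2017 | Q3 2024 (no lag) | 7.7 |

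**Model.** T is time to discontinuation, assumed exponential with mean m. C is time from start to data end. The protocol's duration is min(T, C). With starts uniform over W:

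- reported mean = m − (m²/W)(1 − e^(−W/m))
- share still on drug at data end = (m/W)(1 − e^(−W/m))
- reported share with at least t years = e^(−t/m)(1 − t/W); true share = e^(−t/m)

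**France, m = 10, uniform starts.** e^(−0.714) = 0.490.

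- Mean: 10 − (100/7.14)(0.510) ≈ 2.9 years.
- Still on drug: (10/7.14)(0.510) ≈ 71%.
- At least 2 years: 0.819 × (1 − 2/7.14) = 59%, against a true 82%.
- Under 1 year: 1 − 0.905 × (1 − 1/7.14) = 22%, against a true 9.5%.

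**France, m = 10, strongly front-loaded starts** (start = W × Beta(1,3), so P(C ≥ t) = 1 − (t/W)³).

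- Mean: 4.1 years.
- At least 2 years: 0.819 × (1 − 0.022) = 80%, against 82%.
- Under 1 year: 9.8%, against 9.5%.

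The category bias almost disappears, but the bias in the mean does not.

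**Sensitivity to m, France.** For m = 5, 10 and 20 years the reported mean is 2.3, 2.9 and 3.2 years with uniform starts, and 3.2, 4.1 and 4.7 years with strongly front-loaded starts.

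**All four sources, weighted 87/10/11/20.** 'Mild' means milder front-loading (start = W × U², U uniform).

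| Annual discontinuation | True mean (y) | Reported mean, uniform / mild | Still on drug, uniform / mild | True share ≥2 y | Reported ≥2 y, uniform / mild |
|---|---|---|---|---|---|
| 5% | 19.5 | 3.2 / 4.2 | 83% / 79% | 90% | 65% / 77% |
| 10% | 9.5 | 2.9 / 3.6 | 70% / 62% | 81% | 59% / 69% |
| 20% | 4.5 | 2.3 / 2.8 | 50% / 39% | 64% | 46% / 54% |
| 30% | 2.8 | 1.8 / 2.1 | 36% / 25% | 49% | 35% / 42% |

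The reported mean is short in every row.

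**Ceiling.** If every patient started at launch and never stopped, the weighted mean would be (87×7.14 + 10×9.46 + 11×5.71 + 20×7.7)/128 ≈ 7.3 years.

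**Country comparison.** With m = 10 and uniform starts in both, Germany reports 2.4 years and Denmark 3.5 years. Only the window differs.

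**The case against.** The study is descriptive. Exposure is defined inside the study window, and no decision rule uses the mean. As a description of observed exposure the mean is valid, and the protocol never calls it persistence. A SAP that is not shown may add counts of ongoing patients or a time-to-event summary. This stands, and it lowers the severity. It does not remove the point, because section 9.7.3.2 itself states the summary for an objective worded as estimating duration of therapy.

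Several stronger readings are tempting, but the documents do not support them.

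- *Most patients will still be on treatment, so the endpoint only measures length of observation.* The documents say the indication is long-term and give no discontinuation rate. Under the assumptions above, most patients are ongoing only up to about 15–20% annual discontinuation with uniform starts, or just under 15% with mild front-loading. Above that, real stops drive much of the value.
- *The under-1-year share will look like early discontinuation.* That depends on the start pattern; with strongly front-loaded starts the distortion is negligible.
- *German data end in 2020.* Section 9.2.1 gives this as a conditional example, section 9.4 says the lag can be up to two years, and section 6 lets the end of data collection be adjusted. It is a worst case.
- *Section 9.1 sets a rival follow-up rule.* Section 9.2.1 makes clear that the end varies by source, so section 9.1 is loose wording to align.

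One feature works the other way. Exposure runs from first to last prescription, so treatment gaps count as use and partly offset the bias.

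**Conclusion.** The point holds as a should-fix. Patients ongoing at data end are counted as completed durations, so the mean understates duration of therapy whenever any patient is ongoing. That direction needs no discontinuation rate. It concerns censoring alone; treatment gaps counted as use could offset part of it.

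The size cannot be settled from the protocol. The figures rest on exponential time on drug, assumed start patterns and assumed data-end dates. For the mean the shortfall is large when discontinuation is low and smaller when it is high. For the category shares it ranges from material to almost nothing. The country distortion is real in direction, but the Germany–Denmark example uses the longest German lag.

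The result-dependent categories are a separate, smaller weakness. They should not be read as part of the censoring bias.

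**What to change.** 1. Label the mean in section 9.7.3.2 as observed exposure time.
2. For each source, report the number still on treatment at data end and the potential follow-up (start to last complete data date).
3. Add Kaplan-Meier persistence at 1 and 2 years with 95% confidence intervals. Define discontinuation for the analysis by a prespecified permissible gap after the end of supply; without one, a patient a few days late at data end would count as a stop. Censor at the source's last complete data date, and state how death and loss of coverage are handled.
4. Apply the small-cell masking of section 10.4 to these outputs. State that intervals will be wide in the sources with 10 to 20 expected patients.
5. Prespecify one set of duration categories for all sources and delete the sentence that lets them change with results.
6. Align section 9.1 with section 9.2.1, so that follow-up ends at each source's data end.

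The cost is protocol or SAP wording and one standard procedure per source. No new data are needed.

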9.7.3.3 Concomitant Medications

To analyse the use of concomitant medications, two study periods will be determined:

- 1. The one-year period before the first delivery of eliglustat.
- 2. The period during eliglustat use which will span from the first delivery of eliglustat to the last delivery of eliglustat plus the duration of supply.

The analyses described in the following sections will be conducted separately for each of the two periods.

9.7.3.3.1 **Proportion of Patients with CMI**

Proportion of patients with CMI will be computed considering all CMI, by therapeutic class of CMI (CMI1 to CMI7), and separately for the group of CYP inhibitors (CMI1 to CMI4). Also, proportion of patients that have taken a strong or moderate CYP2D6 inhibitor simultaneously with a strong or moderate CYP3A inhibitor will be explored, if feasible.

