9.3.2 Outcomes of Interest

Outcomes of interest include concomitant medication use in terms of therapeutic class and duration. The CMI are strong and moderate CYP2D6 inhibitors, strong and moderate CYP3A inhibitors, strong CYP3A inducers, P-gp substrates and CYP2D6 substrates. Simultaneous use of strong or moderate CYP2D6 inhibitors with strong or moderate CYP3A inhibitors concomitantly with eliglustat will be explored, if feasible. Other outcomes will be the prescriber's specialty and the type of patient visit (e.g., hospital or in outpatient settings).

Concomitant medication use will be identified using ATC codes available in each database.

The duration of drug use will be defined with a continuous variable (number of days) and also with a categorical variable. The categorical variables will be defined as follows: 1. Total use of concomitant medication will be defined as any prescription whatever the duration; 2. Chronic use of concomitant medication will be defined as total duration of single or consecutive prescriptions of 15 days or over.

Where information is available, and subject to Ethics Committee approval, data on prescriber's specialty will be defined as the specialty of doctors prescribing concomitant medications to GD1 patients (e.g., GPs, haematologists, neurologists, etc.). These data will enable to define the number and profile of health professionals managing these patients. Data on the type of patient's visit is intended to capture whether prescriptions of concomitant drugs to GD1 patients are written in hospital or in outpatient settings.

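### The proportion of patients with a CMI is computed over one fixed year before eliglustat and over an uncapped, patient-specific period during it, so the second figure depends on exposure length

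*Protocol*

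**What the plan says.** Section 9.7.3.3 defines two periods. The first is "The one-year period before the first delivery of eliglustat". The second is the period of eliglustat use, "which will span from the first delivery of eliglustat to the last delivery of eliglustat plus the duration of supply". The analyses are run separately in each, and 9.7.3.3.1 applies one measure to both: "Proportion of patients with CMI will be computed considering all CMI, by therapeutic class of CMI (CMI1 to CMI7".

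Section 9.3.2 defines what counts as use: "Total use of concomitant medication will be defined as any prescription whatever the duration". The second category is "Chronic use of concomitant medication will be defined as total duration of single or consecutive prescriptions of 15 days or over". For duration, 9.7.3.3.2 adds up the days of all deliveries in a CMI category for each patient and averages the totals. Neither section gives a person-time denominator, a fixed window or a truncation for the second period.

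Patients are "followed from one year before their first prescription of eliglustat to the end of the study in Q3 2024" (section 9.1), subject to the data lag in each source. Section 9.7.1 offers analyses by year, with trends in proportions, only if patient numbers allow. On the results by data source it says: "This will allow to compare the drug availability and prescribing patterns between European countries". Sections 7.3 and 8 say that the study will allow the effectiveness of the risk minimisation measures to be assessed.

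**The concern.** An at-least-one-prescription proportion is cumulative: for a given patient it cannot fall as the window lengthens. Total CMI days grow with time as well; a patient with the same share of days covered collects three times as many days in three years as in one. The pre-period is one year for everyone, while the second period differs by patient and, through launch dates and data lags, by country.

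Two readings of the results are at stake. Set side by side, the before and during figures invite the question whether interacting drugs are avoided once eliglustat starts, and a real fall in prescribing could appear as a rise. Across data sources, a difference in the during figure could reflect length of exposure rather than prescribing.

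**Working it through.** **Figures in the plan.** There is no power calculation to reproduce. The expected minimum size adds up: 87 + 10 + 11 + 20 = 128 (section 9.5). So does the pilot proportion of CYP inhibitor users: 10/48 = 20.8% (Appendix 3).

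**Longest possible second period.** This is the time from launch date (section 9.4) to last available data, taking the end of Q3 2024 as 30 September 2024.

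| Source | Launch | Data end | Ceiling (years) | Expected patients |
|---|---|---|---|---|
| Germany | 15 April 2015 | 2020 to 2022 (lag up to two years; extraction 2022 to 2024) | 5.7 to 7.7 | 11 |
| France | 9 November 2016 | December 2023 (year N available in N + 1) | 7.1 | 87 |
| Israel | 12 January 2017 | September 2024 (no lag) | 7.7 | 20 |
| Denmark | April 2015 | September 2024 (no lag) | 9.5 | 10 |

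These are ceilings. The protocol gives no expected mean exposure, and typical exposure will be shorter.

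**Effect of window length.** The protocol gives no one-year CMI proportion, so p = 20% is assumed.

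- Constant rate: P(any CMI in t years) = 1 − (1 − p)^t. A halved rate replaces t by t/2.
- Patients differing in their rate (gamma, variance θ = 2): P = 1 − (1 + θmt)^(−1/θ), with m set so that P = 20% at one year: m = (0.8^(−2) − 1)/2 = 0.281. A halved rate replaces m by m/2.

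| On eliglustat | Constant rate, 3 y | Constant rate, 5 y | Gamma, 3 y | Gamma, 5 y |
|---|---|---|---|---|
| Rate unchanged | 1 − 0.8^3 = 48.8% | 1 − 0.8^5 = 67.2% | 39.0% | 48.8% |
| Rate halved | 1 − 0.8^1.5 = 28.4% | 1 − 0.8^2.5 = 42.8% | 26.4% | 35.5% |

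In both models the halved rate gives a figure above the pre-year's 20% as soon as t exceeds 2 years, because t/2 is then greater than 1. For short exposure the direction reverses: at six months an unchanged rate gives 1 − 0.8^0.5 = 10.6%.

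**Range of assumptions, unchanged rate.**

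- One-year proportion 10%: 27% at 3 years, 41% at 5.
- One-year proportion 5%: 14% at 3 years, 23% at 5.
- Pilot 20.8% read as a five-year figure, as the footnote to its Table 4 implies: 4.6% per year, hence 13% at 3 years.
- One-year proportion 20.8% with very strong heterogeneity (gamma variance 5): 33% at 3 years, 39% at 5.
- Limiting case of permanent users only: 20% in both periods, no rise.

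**The case against.** The strongest reply is that the study is descriptive. Section 9.1 says it has no comparative elements, and no difference, ratio or test between the periods is planned. The share of patients ever exposed to an interacting drug while on eliglustat is also a legitimate quantity for the stated objective. Section 9.7.3.2 reports mean exposure with dispersion and duration categories, so readers will see how long patients were treated. Analyses by year are foreseen and are most plausible in France, with 87 expected patients. The protocol defers detail to a separate SAP, which is not among the documents and could add person-time scaling.

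Much of this stands, and it rules out several stronger readings. A reader might infer that the pre-year is the formal benchmark for risk minimisation; no section says so. A reader might take about nine years as the usual exposure; it is a ceiling for Denmark only, with 10 of 128 expected patients. A reader might conclude that sources with longer data will look worse; maximum windows are not average exposure, and patients treated under a year are biased downward. Nor can the size of the rise be read from the protocol, since many listed drugs may be taken long term and persistent users add nothing in later years.

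It does not remove the problem. The two windows and the measure are fixed in the protocol itself, the by-year analyses are conditional and unlikely with 10, 11 or 20 patients, and section 9.7.1 does announce a country comparison.

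**Conclusion.** The point holds as a matter of measurement. Followed exactly, section 9.7.3.3 gives during figures that mix CMI use with length of exposure, and neither the before and during pair nor the country figures can be read without separating the two.

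Under an assumed 20% yearly probability, unchanged use would read about 39% to 49% at 3 years and a halved rate about 26% to 28%, so a real improvement could look like a worsening. These sizes rest on the assumed rate and repeat-use pattern. Lower rates give smaller rises, and mostly persistent users give little or none. The dependence on exposure length comes from the definitions; its size in these patients is unknown.

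**What to change.** - **9.7.3.3.1:** for each data source, add the cumulative proportion of patients with at least one CMI in the first 12 months on eliglustat. Estimate it by Kaplan-Meier with censoring at the end of exposure, so that short-term users stay in, subject to the small-cell rules of section 10.4. Set this figure beside the 12-month pre-period, among patients with a full recorded pre-year, and use it for country comparison.
- **9.7.3.3.2:** add the percentage of observed days covered by a CMI in each period.
- **Whole-period proportion:** keep it, label it as cumulative, and show person-years and median exposure next to it.
- **Do not substitute CMI users per 100 patient-years.** Each user counts once while the denominator grows. If 20 of 100 patients are permanent users, the pre-year gives 20 per 100 patient-years and five years on eliglustat give 20/500, or 4 per 100: an apparent fall of 80% with no change in use.

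The cost is protocol and SAP wording and a little extra programming on dates already extracted. Patients without a full recorded pre-year leave the matched comparison, and estimates in the smaller sources may be partly suppressed.
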